5.3 Subgroup analyses

If the sample size permits, the investigators will conduct subgroup analysis in different subpopulations for the primary and secondary outcomes. The investigators will create the following subgroups in our MTP study:

- Subgroup 1: subdivide the population into two groups: with or without isolated severe traumatic brain Injury (TBI) with AIS HEAD ≥ 3 and AIS thorax/abdominal <3 and/or AIS lower extremity < 4 .
- Subgroup 2: subdivide the population into two groups: with or without anticoagulation treatment before trauma.

- Subgroup 3: subdivide the population into two groups: with or without trauma-induced coagulopathy.
- Subgroup 4: subdivide the dataset in prehospital settings and in-hospital settings.
- Subgroup 5: All analysis and results will be present into two subgroups: missing data imputed and missing data excluded with the complete case analysis.
- Subgroup 6: The investigators will test the heterogeneity of the performance parameters of each centre and the investigators will potentially exclude data from centre with homogeneous case mixes.
- Subgroup 7: subdivide the population into two groups: low-volume prehospital fluid replacement (<1500 ml) and High-volume prehospital fluid replacement (>1500ml).

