
Objective(s):
	
 - External validation of pre-existing prognostic scores of traumatic haemorrhages at different times of care (Scene of Injury, admission at the trauma room) in order to assess their overall performance, discrimination and calibration in the prediction of massive transfusion and haemorrhagic death. - Comparison of score performances (Overall performance, discrimination and calibration).

Outcome(s):
	
Primary study outcome :
 
 - Massive transfusion defined by a transfusion equal to or greater than 10 Red blood cell (RBC) / 24 hours or ≥ 3 RBC in the first hour if available in the Swiss Trauma Registry. 
Secondary study outcome :
 
 - Death due to bleeding (if available in the registry) - Early death (< 24 hours) - Coagulopathy at admission defined by INR > 1.2, quick TP < 70% or Fibrinogen < 1.5 g/L (6,7,8)

Study design:
	
Observational non-interventional study based on a multicentric anonymized registry

Inclusion / Exclusion criteria:	
Study population: All adult trauma patients treated at twelve Swiss trauma centres Level I from 01.01.2015 to 31.12.2019 with eligible criteria of the Swiss Trauma Registry (STR) are included. All data from the register are anonymised without any access to medical files. The identity of the trauma patients, date of birth, address and trauma scene location are unknown (as mandatory by the swiss law: Art. 2 ORH).
 
Inclusion criteria:
 
- Age > 16 years old- ISS (Injury Severity Score) ≥ 16 and/or AIS head (Abbreviated Injured scale) ≥ 3 
Exclusion criteria:
 
- Age < 16 years old- ISS < 16 and or AIS < 3- Isolated Burns (including electric shock) or if the burn is clearly the primary injury- Patients arriving at the trauma room with no sign of life and no diagnostic/therapeutic measures have been initiated for them- Choking or hanging patient without any other injury.- Drowning patients
--	---

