
Measurements and procedures:
	
Predictive Variables:
 
Demographics: Age, gender, type of accident, mechanism of Injury (penetrating/blunt), Hospital (anonymised by number), Date and time of accident.
 
Prehospital settings: Arrival on scene (paramedics, date/time and medics, date/time), type of transport: physician staffed ambulance/helicopter, Firsts clinical measures recorded: Systolic blood pressure (SBP), Respiratory rate (RR), Heart Rate (HR), Pulse Oximetry, Glasgow coma scale, temperature, cardiopulmonary reanimation, Drugs Use: Tranexamic acid (Date/time) and vasoactive, early death before arriving to the hospital.
 
In-hospital settings (trauma room): Hospital arrival (date/hour), Firsts measures: Systolic blood pressure (SBP), Respiratory rate (RR), Heart Rate (HR), Pulse Oximetry, Glasgow coma scale, temperature, cardiopulmonary reanimation, Biological parameters: haemoglobin, Platelets, lactates, Base excess, TP (sec and %), INR, PTT, Fibrinogen, Drugs use: Tranexamic acid (date/time), vasoactive, Vitamin K, Fibrinogen, Prothrombin complex concentrate, rFVIIa, Red blood cell (number in the first hour, date/hour of each Red blood cell), platelets units, fresh frozen plasma.
 
Imaging: type of imaging, results: positive or negative for free fluid, date/time of imaging.
 
Diagnosis: AIS final, ISS final, Medical past, use of anticoagulant/antiaggregant before trauma
 
Outcome: Date/time of death, Early death (<12 hours), Early death (<24 hours), number of red blood cell in 24 hours, Massive transfusion (defined as ≥ 10 red blood cells in the first 24 hours).
 
Depending of the availability of requested variables in the registry, we will ask for complementary variables.
 
Comparison:
 
Performance comparison of pre-existing scores (TASH, ABC and BATT scores) in term of overall performance, discrimination and calibration.
 
Evaluation of clinical utility and feasibility in prehospital settings and emergency admission.

Intervention:
	
Comparison of score performances (Overall performance, discrimination and calibration)

Control Intervention (if applicable):
	
No group controls

Number of Participants with Rationale:
	
The number of participants will depend of the Swiss Trauma Registry Database. We project to include 10'000 participants for our study. A post-hoc power calculation will be performed.

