3.2 Sample Size and Power consideration

As his study is retrospective, the sample size is fixed. The number of participants will depend on the STR Database. The investigators anticipate using the data of 10'000 participants included in the Swiss Trauma Registry from 1st January 2015 to 31st December 2019. A post-hoc power calculation will be performed.

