5.2.3. Discrimination

Discrimination is the ability of the score to correctly identify patients with the outcome. The investigators will estimate the sensitivity, specificity, positive and negative likelihood ratio for the defined threshold of each score (ABC, TASH, BATT).

The likelihood ratio is the likelihood of a positive score in a patient with the outcome compared to the likelihood of a positive score in a patient without the outcome. The positive likelihood ratio is the ratio of sensitivity to 1-specificity. The negative likelihood ratio is the ratio of 1-sensitivity to specificity. A positive likelihood ratio of 10 or above will result in a large increase in the probability of the outcome. A negative likelihood ratio of 0.1 or less will result in a large decrease in the probability of the outcome.

The investigators will plot the Receiving Operating Characteristic (ROC) curve which is the sensitivity (true positives) on 1-specificity (false positives) for each defined threshold of each

score. An ideal score will reach the upper left corner (all true positive with no false positive). The investigators will estimate the area under the ROC curve (AUROC) that corresponds to the concordance statistic (C-Statistic) for binary outcome. A C-statistic of 1.0 shows perfect discrimination ability.

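### Centre enters the plan only through an unspecified heterogeneity test and an undefined option to exclude centres, which is a weak basis for judging transportability across the twelve hospitals

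*SAP*

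**What the plan says.** The protocol synopsis covers "All adult trauma patients treated at twelve Swiss trauma centres Level I from 01.01.2015 to 31.12.2019". SAP 4.1 (Screening Data) names the same twelve hospitals. SAP 3.2 sets no target: "The investigators anticipate using the data of 10'000 participants included in the Swiss Trauma Registry", and "A post-hoc power calculation will be performed". Neither document gives a massive transfusion rate or the number of patients per centre.

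The main analyses are in SAP 5.2.1 to 5.2.4, and the secondary outcomes are to be analysed in the same way. These sections define the Brier score, sensitivity, specificity, likelihood ratios, AUROC, P/O, and calibration intercept and slope. Centre is mentioned in none of them, and no standard error or confidence interval method is named. The list of imputation variables (under Missing Data, Imputation method) does not contain centre.

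Centre appears once, in SAP 5.3, whose list opens: "If the sample size permits, the investigators will conduct subgroup analysis in different subpopulations". Subgroup 6 reads "The investigators will test the heterogeneity of the performance parameters of each centre", and the sentence goes on to allow possible exclusion of centres with a homogeneous case mix. The test, its level, a measure of heterogeneity, the meaning of a homogeneous case mix and the consequence of the result are all left open.

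The protocol (Measurements and procedures) requests the hospital as an anonymised number. SAP Table 1, which is meant to list every variable requested, has no centre row.

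**The concern.** The study asks whether existing scores hold up in Swiss practice. The SAP Discussion speaks of transportability to the registry and of activating massive transfusion from the scene. For that purpose the spread of performance between hospitals matters as well as the average. The primary outcome is a count of units given, so it partly reflects local transfusion practice, and calibration could plausibly differ from one hospital to another.

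A heterogeneity test returns a p-value. It does not say how far centres differ, nor what a hospital adopting a score should expect. With few events per centre it can miss differences that matter.

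The exclusion option raises a separate problem. With no definition, the decision to remove a centre would be made after its results are known, and it could change the pooled estimates. That sits badly with the SAP's own aim, in its Conclusion, of limiting data-driven results.

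**Working it through.** **No planned figure to reproduce.** The 10'000 is a projection of registry size, with no event rate, power or precision behind it. What follows is the power of the Subgroup 6 test under stated assumptions.

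**Inputs from the documents:** 12 centres; 10'000 patients.

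**Assumptions:** equal centres; massive transfusion rate p = 3% (range 1% to 10%); AUROC A = 0.85; Cochran's Q at 5% with 12 − 1 = 11 degrees of freedom (critical value 19.68); between-centre SD (tau) of 0.03 or 0.05 for AUROC, and 0.2 or 0.3 for log P/O.

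**Events per centre.** 10'000/12 = 833 patients. At 3% that is 25 events and 808 non-events. At 1% it is 8 events, and at 10% it is 83.

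**Standard error of one centre's AUROC (Hanley-McNeil).**
- q1 = A/(2 − A) = 0.7391; q2 = 2A²/(1 + A) = 0.7811; A² = 0.7225.
- Variance = [A(1 − A) + 24(q1 − A²) + 807(q2 − A²)]/(25 × 808) = (0.128 + 0.399 + 47.3)/20'200 ≈ 0.00237.
- SE = 0.049, so one centre's 95% interval is about ±0.095.

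**Standard error of one centre's log P/O.** sqrt((1 − p)/events) = sqrt(0.97/25) = 0.197.

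**Power of the test.** P(chi-square with 11 df > 19.68/(1 + tau²/SE²)).
- AUROC, tau 0.03: 19.68/(1 + 0.0009/0.00237) = 14.3, power 22%.
- AUROC, tau 0.05: 19.68/(1 + 0.0025/0.00237) = 9.6, power 57%.
- Log P/O, tau 0.2: 19.68/(1 + 0.04/0.0388) = 9.7, power 56%.
- Log P/O, tau 0.3: 19.68/(1 + 0.09/0.0388) = 5.9, power 88%.

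**What these SDs mean.** An AUROC SD of 0.03 puts 95% of centres between 0.85 ± 1.96 × 0.03, or 0.79 to 0.91. A log P/O SD of 0.2 puts them between exp(±1.96 × 0.2), or 0.68 to 1.48. An SD of 0.3 gives 0.56 to 1.80.

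**Power by assumed massive transfusion rate:**

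| Rate | Events per centre | AUROC SD 0.03 | AUROC SD 0.05 | log P/O SD 0.2 | log P/O SD 0.3 |
|---|---|---|---|---|---|
| 1% | 8 | 10% | 21% | 20% | 43% |
| 2% | 17 | 15% | 40% | 39% | 73% |
| 3% | 25 | 22% | 57% | 56% | 88% |
| 5% | 42 | 36% | 79% | 79% | 97% |
| 8% | 67 | 54% | 92% | 93% | >99% |
| 10% | 83 | 64% | 96% | 96% | >99% |

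**Unequal centres.** At 3%, with an assumed split giving 6 to 48 events per centre, simulated power is 21%, 55%, 54% and 85% for the same four columns. The equal-size assumption hardly matters.

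**The case against.** A reader might infer three stronger points. The documents do not support them.

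1. *The test will usually miss material differences.* This fits small variation in AUROC but is not general. At the assumed 3%, power is 88% for a log P/O SD of 0.3 and 92% for an AUROC SD of 0.08, and at 5% and above it is good for most of the larger values. The 25 events per centre is itself an assumption.

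2. *The pooled intervals will be too narrow.* The SAP names no interval method, so there is none to criticise. The answer also depends on the target. Suppose the twelve centres are a sample from a wider population, with 300 events in total. The naive relative SE of P/O is 1/sqrt(300) = 5.8%, against sqrt((tau² + 12/300)/12) = 8.2% at tau 0.2 and 10.4% at tau 0.3. A nominal 95% interval would then cover 83% or 72%. But SAP 4.1 describes the registry as representing the Swiss trauma system and names these twelve centres. With them taken as fixed, a simulation at tau 0.3 gave about 95% coverage for the naive interval. A pooled estimate that ignores centre is therefore defensible for these hospitals. Making a random-effects interval the main one, or resampling only twelve centres (a percentile bootstrap covered 90% in the same setting), is debatable.

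3. *The centre analysis is optional.* The sample-size condition heads the list, but the list also holds items planned unconditionally elsewhere, such as the imputed and complete-case results. Whether the condition governs Subgroup 6 is unclear.

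It is also fair to say that the plan does look at centre, and that nowhere does it say a non-significant test would be read as equal performance. What remains is that the plan provides for no estimate of between-centre spread, and that the exclusion option has no rule.

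**Conclusion.** The point holds as a gap in how centre is analysed. It does not show that the pooled estimates are wrong. Centre is confined to one subgroup item whose test is unspecified and whose exclusion option is undefined; neither the main analyses nor the imputation list uses it. With 12 equal centres, 10'000 patients and an assumed 3% event rate, the test's power runs from 22% to 57% for AUROC SDs of 0.03 to 0.05, and from 56% to 88% for log P/O SDs of 0.2 to 0.3. Over event rates of 1% to 10% the same four cases span 10% to over 99%. Power therefore cannot be relied on before the event rate is known, and even a well-powered test would not report how large the differences are. The change is worth making before the data arrive, chiefly because transportability is what the study sets out to show.

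**What to change.** Keep the overall pooled estimates in SAP 5.2. In Subgroup 6, replace the test as follows.

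- Report the C-statistic by centre for each score.
- Report P/O and calibration intercept and slope by centre wherever a score supplies predicted probabilities for that outcome. For massive transfusion this excludes BATT, as SAP 5.2.4 itself says, and it excludes ABC as documented, since Figure 2 gives only a cut-off. BATT can be included for death due to bleeding or early death.
- Summarise across centres with a random-effects model, giving the between-centre SD and a 95% prediction interval for a new centre. Where events are few, use partial pooling through a mixed logistic recalibration model.
- Add the centre number to SAP Table 1, in line with the protocol's request. If centre estimates are made on imputed data, add centre to the imputation list too.
- Delete the exclusion of centres by case mix, or define it now as a sensitivity analysis with a stated criterion, reported beside the result for all centres.
- State whether Subgroup 6 depends on sample size and, if so, the threshold.

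The cost is SAP wording and a little more analysis, using a variable the protocol already requests. Intervals for centres with few events will be wide, and with twelve centres the between-centre SD will itself be imprecise.

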
Study Duration:
	
11 months

Study Schedule:
	
From August 2020 to June 2021

Investigator(s):	
[name] Study Director Service des Urgences Centre hospitalier Universitaire Vaudois (CHUV) [name] [name] Email : [contact]
 
Doctor [name] Study Director Service des Urgences Centre hospitalier Universitaire Vaudois (CHUV) [name] [name] Email : [contact]
 
[name] Principal investigator Service des Urgences Centre hospitalier Universitaire Vaudois (CHUV) [name] [name] Email : [contact]

Study Centre(s):	
Multi-centre study including 12 Swiss Trauma Centre included in the Swiss Trauma Registry (Centre Hospitalier Universitaire Vaudois, Hôpitaux universitaire Genevois, Inselspital Bern, Universitätsspital Basel, Universitätsspital Zürich, Kantonsspital St. Gallen, Luzerner Kantonsspital, Kantonsspital Aarau, Kantonsspital Graubünden, Kantonsspital Winterthur, EOC – Ospedale Regionale di Lugano, Gesundheitsnetzwerk Wallis – Standort Sion)

Statistical Considerations:	
Comparison between scores:
 
 - Overall performance: Brier score - Discrimination: C-statistic, AUROC curve and calculation of likelihood ratio, sensitivity and specificity. - Calibration: Global calibration, calibration curve with intercept and slope calibration. 
Missing data: To estimate baseline risk for the full dataset, we will replace missing predictors using multiple imputation by chained equation.
 
Please referring to the Statistical Analysis Plan

GCP Statement:	
This study will be conducted in compliance with the protocol, the current version of the Declaration of Helsinki, the ICH-GCP or ISO EN 14155 (as far as applicable) as well as all national legal and regulatory requirements.

Study Procedure/Flowchart with Timelines: Study specific Examinations have to be clearly identified

1st step :Request database to the Swiss trauma registry, redacting the statistical analysis plan and study registration on Clinicaltrials.org (August-September 2020)

2nd step: Statistical Analysis (October 2020)

3rd step: Results (December 2020)

4th step: Publication

Storage of Data-and Samples for Future Research Aims: no**Ethical Considerations:**

1. Please describe the potential gain of new knowledge obtained with this study, and its meaning for patients/society.

Answer n°1:

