5.4 Statistical Software

All analyses will be performed using STATA software (version 16.0; Stata Corp, College Station, TX, USA).

6. Discussion

Due to the study population (STR), which is partly integrated into the German DGU-Register, the investigators expect good transportability of the TASH score to the Swiss Trauma Registry in terms of overall performance, discrimination and calibration. The ABC score should show lowers results in terms of discrimination due to its validation on small cohorts exclusively in North America. The new BATT score predicting death due to bleeding has been validated on a large English cohort of more than 100,000 patients. It identifies all patients with haemorrhage and not only patients who have received a massive transfusion subject to survival bias. In this context, the BATT score provides good discrimination with only simple physiological variables available at the trauma scene. In case of its external validation on the STR as part of our study, its feasibility would make its clinical utility superior to other pre-existing scores, while identifying a greater number of patients requiring early management. Its application would activate a massive transfusion plan directly at the trauma scene and save precious time.

7. Conclusion

This SAP presents the principles of analysis of the MTP study and discusses its major methodologic and statistical concerns. The investigators hope that the results of the MTP study will be as transparent and robust as possible, so that the investigators minimised the risk of outcome reporting bias and data-driven results.

8. Tables and Figures

Table 1. Overview of all variables requested from the STR for the MTP study.

Variable	Prehospital	In-hospital Trauma room	First 24 hours
Demographics			
Age	X		
Gender	X		
Type of accident	X		
Mechanism of Injury	X		
Accident date	X		
Accident time	X		
Medical past	X		
Arrival on scene (paramedics, date/time)	X		
Arrival on scene (medics, date/time)	X		
Physician Staffed Ambulance (yes/no)	X		
Hospital Arrival (date/time)		X	
Clinical examination (first measures recorded)			
Heart Rate	X	X	
Systolic blood pressure	X	X	
Respiratory rate	X	X	
Pulse oximetry	X	X	
Temperature	X	X	
Glasgow Coma Scale	X	X	
Cardiopulmonary Reanimation	X	X	
Biological parameters			
Haemoglobin		X	
Platelets		X	
Lactates		X	
TP		X	

INR		X	
PTT		X	
Fibrinogen		X	
Base excess		X	
Therapy			
Vasoactive drugs (doses, type)		X	
Tranexamic acid (doses, date/time)	X	X	

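### SAP 5.3, Subgroup 6 allows centres to be excluded on an undefined, discretionary criterion and does not confine this to a sensitivity analysis beside the all-centre result

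*SAP*

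**What the plan says.** SAP 5.3 opens with a condition: "If the sample size permits, the investigators will conduct subgroup analysis in different subpopulations for the primary and secondary outcomes". Under Subgroup 6 the investigators will "test the heterogeneity of the performance parameters of each centre" and will "potentially exclude data from centre with homogeneous case mixes". Both steps stand in one sentence.

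The SAP gives no measure of case-mix homogeneity, cut-off, maximum number of centres, heterogeneity test or pooling model. It does not require the decision to be made without sight of performance, and it does not say whether the all-centre result will be shown as well.

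Related text:
- The protocol synopsis describes a "Multi-centre study including 12 Swiss Trauma Centre included in the Swiss Trauma Registry". SAP 4.1 lists the same 12, and the exclusion criteria in SAP 4.2.2 do not mention centres.
- SAP 5.2.3 will "estimate the area under the ROC curve (AUROC) that corresponds to the concordance statistic (C-Statistic) for binary outcome", with no stratification or pooling by centre.
- On size, SAP 3.2 says "The investigators anticipate using the data of 10'000 participants included in the Swiss Trauma Registry" and "A post-hoc power calculation will be performed". No event rate or precision target is given.
- The SAP's Conclusion (section 7) says the investigators have "minimised the risk of outcome reporting bias and data-driven results".

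**The concern.** An external validation should show how the scores perform across the population it names, here the twelve level I centres. Subgroup 6 lets that population shrink by discretion.

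SAP 3.3 places registration of the SAP before receipt of the dataset. Since the registered text contains no criterion, any criterion actually applied would be chosen later, possibly with centre-level performance already in view. The spread of case mix bears directly on the C-statistic: other things equal, a narrower range of risk gives a lower value. Selecting centres on case mix is therefore not neutral for the quantity being validated. Nor would the reported confidence interval show that a selection had been made.

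An open exclusion of this kind does not fit the claim in section 7 about data-driven results.

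**Working it through.** **No figure to reproduce.** The plan gives no event rate, target C-statistic or heterogeneity threshold. The question is how far the clause could move the estimate.

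**Inputs from the documents.** N = 10,000 (SAP 3.2, a projection) and 12 centres (protocol synopsis; SAP 4.1).

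**Assumptions not in the documents.** Equal centre size; massive transfusion in about 5%, with other values as a range; three centres dropped; a score equal to a normally distributed linear predictor (LP) with a logistic outcome. LP mean -4, with within-centre SD either 1.6 everywhere or drawn from 1.1 to 2.1.

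**Step 1. Information per centre.** 10,000 / 12 = 833 patients. At 2%, 5% and 10% massive transfusion this is about 17, 42 and 83 events. The Hanley-McNeil variance, with A = 0.85, n1 events and n0 non-events, is

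Var = [A(1-A) + (n1-1)(Q1-A²) + (n0-1)(Q2-A²)] / (n1·n0),

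where Q1 = A/(2-A) = 0.739, Q2 = 2A²/(1+A) = 0.781 and A² = 0.7225.

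- Whole cohort at 5% (500 and 9,500): Var = (0.13 + 8.30 + 556.5) / 4,750,000 = 0.000119, SE = 0.0109, 95% half-width 1.96 × 0.0109 = 0.021.
- Single centre: half-width about 0.12, 0.07 and 0.05 at 2%, 5% and 10%.

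Centre AUROCs will therefore look different even where true performance is the same.

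**Step 2. Dropping three centres by case-mix spread, the stated ground.** Mean change in pooled AUROC over 300 simulated registries, SD varying from 1.1 to 2.1:

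| Mean LP of the narrow centres relative to the others | Change |
|---|---|
| equal | +0.010 |
| 0.5 lower | +0.003 |
| 1 lower | -0.004 |
| 2 lower | -0.017 |

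With identical centres (SD 1.6 everywhere), dropping the three with the smallest observed spread gives only about +0.002.

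**Step 3. Dropping the three lowest-AUROC centres, which the wording does not prescribe but would not prevent.** With identical centres, pooled AUROC rises by about 0.012. No true difference exists, so this is pure selection.

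**Step 4. Range under other assumptions** (400 registries per setting, prevalence 3%, 5% or 10%).
- Identical centres, 1 to 4 lowest-AUROC centres dropped: +0.004 to +0.020.
- SD varying between centres, equal mean LP, 2 or 4 narrowest centres dropped: +0.006 to +0.022.
- Four narrow centres (SD 0.8) with the same mean LP, all dropped: +0.022 to +0.026.
- The same four, with mean LP lower by 1, 2 or 3: -0.006 to -0.009, -0.034 to -0.035, and -0.046 to -0.053.

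**Reading.** Removing narrow centres of similar risk takes out poorly separated patients, so pooled AUROC rises. Removing narrow low-risk centres takes out many easily ranked non-events, so it falls. The documents give no centre-level risk, so the sign cannot be settled in advance.

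**The case against.** The strongest defence is that this is only a subgroup item. It is conditional on sample size, the main population is fixed elsewhere as all 12 centres, and no centre appears among the exclusion criteria. Subgroup 5 in the same list also speaks of excluded data, yet plainly means a parallel presentation, so the word alone does not mean removal from the main analysis. This stands as far as it goes: the SAP does not say that Subgroup 6 alters the headline C-statistic. But Subgroup 5 states that both sets of results will be presented, and Subgroup 6 does not.

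A reader might also infer more than the text supports:

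- **That the clause necessarily inflates the C-statistic.** Step 2 shows falls as well as rises.
- **That the excluded centres are those where the scores discriminate worst.** The stated ground is case mix, not performance. In the varied-spread simulation with equal mean risk, the three narrowest and the three lowest-AUROC centres shared on average only about 1.9 of 3.
- **That performance must be seen before the choice is made.** The two clauses are joined without a stated sequence. The SAP permits that order but does not prescribe it.
- **That intervals become too narrow.** Coverage was not examined, and losing 3 of 12 equal centres leaves 7,500 patients, which widens nominal intervals.
- **That one score would be favoured.** All scores are compared in the same patients, so much of any shift is shared. In a simulation with a second, noisier score, the between-score difference moved by only about 0.003.

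Finally, shifts of 0.010 to 0.012 are smaller than the whole-cohort half-width of 0.021. That is correct, but they are about half of it, and they are avoidable selection that the interval does not describe.

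**Conclusion.** The point holds in a limited form. Subgroup 6 permits discretionary exclusion of centres on an undefined criterion, named alongside a test of centre performance, without restricting it to a sensitivity analysis or promising the all-centre result. The validation set and the C-statistic can then depend on a post-hoc choice, which does not sit with the twelve-centre population or with the SAP's Conclusion.

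With three of 12 equal centres dropped, the plausible effect on pooled AUROC is about +0.010 (narrow centres of equal mean risk), -0.004 to -0.017 (narrow centres 1 to 2 LP units lower), or +0.012 by chance (lowest-AUROC centres). These sizes rest on the assumed prevalence, centre sizes, spread and number dropped. The gap in the text does not depend on them. The change should be made; confidence is medium, because neither the direction nor the effect on the headline estimate is fixed by the documents.

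**What to change.** In SAP 5.3, replace the exclusion clause and state:

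1. All 12 centres stay in every main analysis of every score.
2. AUROC and calibration are reported by centre, with a between-centre heterogeneity summary, for example a random-effects estimate with a prediction interval.
3. Centre exclusion appears only as a labelled sensitivity analysis beside the all-centre result. It is either leave-one-centre-out for all centres, or based on a case-mix spread criterion (such as the SD of the score by centre) fixed before data receipt and judged without outcomes.

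Also list the anonymised centre number in SAP Table 1. The protocol requests it, but the table omits it, and Subgroup 6 cannot be run without it.

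The cost is a few sentences and slightly more analysis, with no new patients. The reported estimate may be less favourable than one from a selected set of centres. The random-effects summary is one suitable choice; items 1 and 3 are what close the gap.
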